5.5.2 Secondary Analyses

Secondary objective variables collected in both treatment groups will be summarized by group utilizing descriptive statistics. Statistical comparisons between groups of continuous variables will utilize the same ANCOVA method discussed above substituting the baseline value of the independent parameter, as well as 2-sample t-tests or non-parametric Wilcoxon Rank Sum tests. The following variables will be analyzed:

1. Change from baseline in PAID-parent (YP and TP) at 3 months
2. Change from baseline in DFCS – parents at 3 and 6 months
3. Change from baseline in BGMC-parents at 3 and 6 months
4. Change from baseline in PAID-child (Y or T) at 3 and 6 months
5. Change from baseline in DFCS-child at 3 and 6 months
6. Change from baseline in BGMC-child at 3 and 6 months
7. Changes from baseline in glycemic control (HbA1c, % BG in target, mean BG, SD BG, and % hypoglycemic events) at 3 and 6 months

Secondary objective variables collected in the Intervention treatment group only (ease of use, satisfaction and preference for using the ACCU-CHEK® Connect DMS System by parents, children, school staff, and HCP) will be summarized by question utilizing descriptive statistics of the numerical scale (mean, standard deviation, range and 95% CI) and the distribution of values (number and % of respondents at each level of response).

All secondary analyses will be performed on both the FAS and ITT populations.

5.6 Safety Analyses

The patient incidence of adverse events will be summarized by intervention group, MedDRA System Organ Class and Preferred Term. Such summaries will be displayed for all AEs, AEs by maximum severity, AEs by strongest causality to study device (and any associated pump devices), and AEs leading to withdrawal of study device. A separate analysis of the patient incidence of symptomatic hypoglycemia, severe hypoglycemia (SAE), and diabetic ketoacidosis (SAE) will also be presented.

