11.6 Safety Analysis

All AEs will be coded using the Medical Dictionary for Regulatory Activities (MedDRA). Only AEs occurring after the start of the ACCU-CHEK [®] Connect Online Diabetes Management System will be included in the AEs tables.

Summaries of incidence rates (frequencies and percentages) of individual AEs by MedDRA System Organ Class and Preferred Term will be prepared. Such summaries will be displayed for all AEs, AEs by maximum severity, AEs by strongest causality to study device (and any associated pump devices), and AEs leading to withdrawal of study device.

Deaths, other SAEs and AEs leading to withdrawal will be listed separately.

Episodes (numbers) of the following AEs will be summarized:

- Symptomatic hypoglycaemia
- Severe hypoglycaemia (SAEs)

Diabetic Ketoacidosis (SAEs)

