13.6 Training of Investigators and Study Site Staff

All Investigators and study staff, authorized to perform study procedures, will receive training on the following aspects of the study:

- Clinical study protocol including:
 - Principles ICH & GCP, Declaration of Helsinki and FDA 21 CFR Parts 11, 50, 54, 56, 803, 812, 814 and 820.30; as applicable, with all local laws and regulations and with the regulatory requirements for source data verification
 - Protocol and study procedures.
 - SAE Reporting procedures including completion of SAE Report Form (eCRF) and/or Malfunction /complaint Reporting procedures
 - Monitoring and Audits.
 - o As necessary for compliant study conduct.
- Study devices:
 - ACCU-CHEK® Connect Diabetes Management System (DMS) and consumables
 - o Smartphones, if applicable.
- Completion of eCRF:
 - o Passwords, Data Entry, Corrections, Query process, and Sign-off.
 - Completion of SAE Report Form and sending to the Sponsor.
 - Documentation of protocol violations and deviations.
 - o Device data upload procedures if applicable
- Completion of Subject Questionnaire electronically by means of provided study laptop (at site) into the study eCRF web based system..
- Completion of HCP Questionnaire electronically by means of the provided study laptop into the study eCRF web based system.
- Procedures for Central Lab (Handbook etc.)

14 Reporting of Protocol Violations and Deviations

For the purpose of this study, the following definitions will be used:

Protocol Violation: a violation that may impact subject safety, affect the integrity of study data and/or affect subject's willingness to participate in the study.

Protocol Deviation: a violation that does not impact subject safety, compromise the integrity of study data and/or affect subject's willingness to participate in the study.

Protocol violations and deviations will be recorded in the eCRF throughout the study, and documented further via the query-system, as applicable.

The Investigator must notify the Sponsor and the reviewing EC of any protocol violations to protect the life or physical well-being of a subject in an emergency as soon as possible but no later than 5 working days after the emergency occurred.

For protocol deviation, only the Sponsor also needs to be notified.

In this study, visit time windows deviations are not considered as protocol deviations.

15 References

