2.1.2 Sample size justification

Change from baseline in PAID-C & T parent, the primary endpoint was used to estimate the sample size requirement for the study. A sample size of 75 per group would be sufficient, with a power of 80% to detect a treatment effect of 0.460 with a significance level of 0.05. Given assumptions of SD of 5 to 16, the sample size would be able to detect treatment group differences of 2.3 (SD=5) to 7.4 (SD=16.0). 100 subjects per group will be enrolled to accommodate attrition.

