4.5 Safety Population (SAF)

The Safety Population (SAF) will be all eligible families that have signed informed consent/assent and exited the study after participating for at least 1 day in the study.

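### The safety tables give crude patient incidence by arm with no observation time, and the SAP drops the episode counts that the protocol promises

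*SAP*

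**What the plan says.** SAP 5.6 sets the measure for the by-arm adverse event tables: "The patient incidence of adverse events will be summarized by intervention group, MedDRA System Organ Class and Preferred Term". For the events of most interest it adds: "A separate analysis of the patient incidence of symptomatic hypoglycemia, severe hypoglycemia (SAE), and diabetic ketoacidosis (SAE) will also be presented". Protocol 11.6 has similar wording: "Summaries of incidence rates (frequencies and percentages) of individual AEs by MedDRA System Organ Class and Preferred Term will be prepared". It speaks of rates, but its own parenthesis makes them percentages of subjects. Protocol 11.6 then goes further for the same three events: "Episodes (numbers) of the following AEs will be summarized". SAP 5.6 does not carry that commitment forward.

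The denominator is the Safety Population of SAP 4.5: eligible, consented families who "exited the study after participating for at least 1 day in the study". Protocol 11.2 simply says all subjects.

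On follow-up, both arms have the same planned 6 months (protocol 2.1). Protocol 6.3 lists the reasons for withdrawal and requires a Study Completion Form with the date and reason. Protocol 6.4 rules out replacement. Protocol 9.5 follows events that are still ongoing, by telephone, for at most 5 days after the last visit. SAP 2.1.2 allows for losses: "100 subjects per group will be enrolled to accommodate attrition". SAP 5.4 and Table 1.6.1 tabulate early discontinuation with reasons, and attendance at each visit, by arm. Nothing in SAP sections 3 to 7 derives or tabulates time under observation.

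**The concern.** Crude patient incidence answers a clear question when everyone is observed for the same time. When some subjects leave early, each brings a full unit to the denominator but less opportunity to contribute an event. If one arm loses more subjects, or loses them sooner, its incidence falls even when the underlying hazard is the same.

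Unequal follow-up is plausible here. Whole sites are randomised 1:1 from a pool of 8 to 13, so an arm may hold as few as 4 sites, and one site with poor retention can shift that arm's average. Families know which system they use. Several withdrawal triggers in protocol 6.3 concern technology: starting a pump, starting CGM, or starting another data-sharing system.

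A second loss is specific to recurrent events. Symptomatic hypoglycaemia can recur many times in one child over six months. Patient incidence scores one episode and ten episodes alike, which is why the missing episode counts matter.

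**Working it through.** **Inputs from the documents.** 75 evaluable and 100 enrolled per group, effect size 0.460, 80% power, two-sided 0.05 (protocol 11.1, SAP 2.1.2). Final visit at week 24 in both arms (schedule of assessments).

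**Assumptions, because the documents give no figure.** The split of drop-out between arms; the proportion *p* with an event over a full 24 weeks; a constant hazard, equal in both arms; exits spread evenly over 24 weeks; no new events captured after exit.

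**1. The plan's own figure.** n = 2 × (1.960 + 0.842)² / 0.460² = 15.70 / 0.2116 = 74.2, rounded up to 75. Then 75 / (1 − 0.25) = 100. The stated size reproduces, and the implied allowance is 25%, not split by arm.

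**2. Observation time.** With drop-out *a*, the fraction of planned person-time observed is (1 − a) + a/2 = 1 − a/2.

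**3. Crude incidence.** Let L = −ln(1 − p). Completers contribute p. Subjects who leave contribute, on average, 1 − p/L. So I(a) = (1 − a)p + a(1 − p/L).

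Worked case, p = 0.50: L = 0.693 and 1 − 0.50/0.693 = 0.279.
- a = 0.15: 0.85 × 0.50 + 0.15 × 0.279 = 0.467
- a = 0.35: 0.65 × 0.50 + 0.35 × 0.279 = 0.423; ratio 0.91
- a = 0.10 and a = 0.40: 0.478 and 0.411; ratio 0.86

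The same formula at a low and a high incidence:

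| Drop-out by arm | Person-time | Crude incidence, p = 5% | Crude incidence, p = 60% |
|---|---|---|---|
| 25% / 25% | 87.5% / 87.5% | 4.38% / 4.38%, ratio 1.00 | 53.6% / 53.6%, ratio 1.00 |
| 20% / 30% | 90% / 85% | 4.50% / 4.26%, ratio 0.945 | 54.9% / 52.4%, ratio 0.954 |
| 15% / 35% | 92.5% / 82.5% | 4.63% / 4.13%, ratio 0.893 | 56.2% / 51.1%, ratio 0.909 |
| 10% / 40% | 95% / 80% | 4.75% / 4.01%, ratio 0.844 | 57.5% / 49.8%, ratio 0.867 |

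**4. Event rate under the same model.** Expected episodes equal hazard × person-time. Dividing by person-time returns the hazard, so the rate ratio is 1.00 in every row.

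**5. Direction.** The ratios are shorter-followed arm over longer-followed arm. If the control arm is the one followed for less time, the device-to-control ratio is the reciprocal: 1/0.91 = 1.10 to 1/0.84 = 1.19. The device would then look less safe than it is.

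**6. Scale against chance.** For 46.7% against 42.3% with 100 per arm, the simple standard error of the difference is √[(0.467 × 0.533 + 0.423 × 0.577)/100] = 0.070. The shift of 4.4 points is smaller than one standard error, before any allowance for clustering.

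**The case against.** The strongest reply is that crude incidence is conventional for descriptive tables in a fixed six-month study of a cleared device. No test of adverse events is planned. The 25% is an enrolment allowance rather than a forecast, and total enrolment may be as low as 150. SAP 5.4 and Table 1.6.1 would already show differential discontinuation, in the same population as the adverse event tables. The table layouts are in a separate document that was not available. All of this is fair, and it limits the weight of the point. It does not close the gap: counts of discontinuation and of attendance do not give time at risk, and readers will compare the columns.

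Four stronger readings are tempting, and the documents do not support them.
- A reader might infer that protocol 6.3 ends event recording at withdrawal. It does not say so; it asks for the withdrawn subject to attend so that documentation is complete. That no new events are collected after exit is inferred from the absence of any such procedure, together with the limited follow-up in protocol 9.5.
- A reader might infer that non-compliance removes only device families. Protocol 6.3 refers to protocol procedures, which bind both arms. The CGM, pump and data-sharing triggers could equally remove control families, who are not given a sharing system.
- A reader might take the adverse event tables for the only between-arm safety comparison. SAP 5.5.2 also compares the percentage of readings below 70 mg/dL between arms (Tables 2.5.6.1 and 2.5.6.2), and that measure has readings as its denominator.
- A reader might blame the visit window, because protocol section 14 does not count departures from it as deviations. The window of ±2 weeks is the same in both arms, and nothing suggests drift that differs by arm.

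It is also true that events per patient-month stay biased if families leave for reasons linked to their risk of events.

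**Conclusion.** The point holds as a gap in safety reporting. Neither document defines observation time for adverse events, and SAP 5.6 relies on patient incidence alone where protocol 11.6 also plans episode numbers for three events. The distortion is conditional: nil at equal drop-out, and a crude ratio of about 0.91 to 0.84 under assumed splits of 15%/35% to 10%/40% with equal constant hazards and evenly spread exits. It may favour either arm. The splits and the incidences are assumptions; only the 25% total follows from the plan. In absolute terms the shift is about half a percentage point for an event with 5% incidence under the 15%/35% split, and 4 to 5 points for one with 50% to 60%. It does not touch the primary analysis. It is worth correcting because the correction is cheap and restores a protocol commitment.

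**What to change.** In SAP 5.6:
- Derive observation time per subject, from Visit 1 to the last adverse event contact or exit, and report the total by arm.
- In Tables 3.1 and 3.3, keep crude patient incidence and add the number of episodes and events per 100 patient-months by arm. For symptomatic hypoglycaemia, severe hypoglycaemia and diabetic ketoacidosis, this restores what protocol 11.6 plans.
- State that the rates assume a roughly constant hazard, do not remove bias from informative drop-out, and are to be read with the discontinuation reasons in Table 1.6.1.
- Settle the starting point while doing this. Protocol 11.6 admits to the tables "Only AEs occurring after the start of the ACCU-CHEK" online system; control subjects have no such start, so the rule and the start of observation time need one definition that applies to both arms.

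The cost is a few lines of SAP text, one derived variable and slightly wider tables. Visit dates already feed the study day in SAP 3.3, and the Study Completion Form holds the date of early discontinuation. No new data collection is needed.

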9.3.1 Expected Adverse Events

9.3.1.1 Captured Expected Adverse Events

The following expected AEs may occur at any time in the course of managing diabetes. Immediate or short term risks to subjects from some of these expected AEs are higher than those identified under Non-Captured Expected AEs.

Therefore, for the purposes of this study, the following expected AEs will be considered captured expected AEs and the AE Form in the eCRF needs to be completed:

- Symptomatic hypoglycemia episodes (see Section 9.2.2).
- Hyperglycemia in combination with medical intervention..
- Ketosis and ketoacidosis.

These captured expected AEs will be handled as follows:

Subjects will be instructed to follow their personal physicians' instructions for management of low and high blood glucose values or otherwise as instructed by the Investigator.

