3.5.2.1 Derived Visit and Visit Intervals

The date of each visit from the eCRF data will be used as a reference date for the dates of BG readings from the subject BG files. Those readings from Diasend download files that occur on or 30 days prior to the baseline visit date will be considered Baseline values. In a similar fashion values between 30 days prior to or on Visit 3 or Visit 4 will be considered Visit 3 or Visit 4 values, respectively.

For Baseline downloads, if there are no readings on the 30th day prior to the visit date, the first day there is a reading will be considered the beginning of the Baseline visit interval. The length of the visit interval for baseline will be calculated as:

$(\text{Baseline Date} - \text{Date of First day of Baseline interval}) + 1$

Post-baseline intervals will be defined as 30 days for the Intervention group, and a similar length of visit interval as defined for Baseline will apply to the Control group.

It will be assumed that the first date reading for each subject using the ACCU-CHEK® Connect DMS System will be entered after training (post-baseline) even if on the same day as baseline.

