3.5.2.2 Derived BG Glycemic Control Parameters

The following derivations will be made from the BG data at each study interval (Baseline, Visit 3, and Visit 4):

- Total number of BG checks during the interval
- SMBG frequency: Average number of daily SMBG measurements per interval will be defined as the total number of BG checks during the visit interval divided by the total number of days in the interval.
- BG Range Flags: Individual BG readings will be flagged as:
 - hypoglycemic reading if < 70 mg/dl (LO)
 - hyperglycemic reading if > 160 mg/dl (HI)
 - within target range 70-160 mg/dl

- Hypoglycemia: Percentage of hypoglycemic measurements defined as the number of hypoglycemic readings in the interval divided by the total number of BG checks in the interval.
- Glucose Target Range: Percentage of Target Range measurements defined as the number of within target range readings in the interval divided by the total number of BG checks in the interval. Values designated as ‘LO’ or ‘HI’ in the meter data will be classified as below or above, respectively
- Glycemic Variability
 - Mean of all BG readings per subject within the interval
 - BG variability (as SD of all glucose readings over the interval)

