Table 2.7.2.2	Exit Questionnaire: Usability Child with Diabetes ITT Population
Table 2.8.1.1	Exit Questionnaire: Satisfaction Parent/Caregiver of Child with Diabetes FAS Population
Table 2.8.1.2	Exit Questionnaire: Satisfaction Parent/Caregiver of Child with Diabetes ITT Population
Table 2.8.2.1	Exit Questionnaire: Satisfaction Child with Diabetes FAS Population

Roche Diabetes Care, Inc

Table No.	Title
Table 2.8.2.2	Exit Questionnaire: Satisfaction Child with Diabetes ITT Population
Table 2.9.1.1	End of Study Questionnaire: Preference Parent/Caregiver of Child with Diabetes FAS Population
Table 2.9.1.2	End of Study Questionnaire: Preference Parent/Caregiver of Child with Diabetes ITT Population
Table 2.9.2.1	End of Study Questionnaire: Preference Child with Diabetes FAS Population
Table 2.9.2.2	End of Study Questionnaire: Preference Child with Diabetes ITT Population
Table 2.10.1.1	School Nurse Questionnaire: Preference FAS Population
Table 2.10.1.2	School Nurse Questionnaire: Preference ITT Population
Table 2.10.2.1	School Nurse Questionnaire: Usability FAS Population
Table 2.10.2.2	School Nurse Questionnaire: Usability ITT Population
Table 2.10.3.1	School Nurse Questionnaire: Satisfaction FAS Population
Table 2.10.3.2	School Nurse Questionnaire: Satisfaction ITT Population
Table 2.11.1.1	HCP Questionnaire: Preference FAS Population
Table 2.11.1.2	HCP Questionnaire: Preference ITT Population
Table 2.11.2.1	HCP Questionnaire: Usability FAS Population
Table 2.11.2.2	HCP Questionnaire: Usability ITT Population
Table 2.11.3.1	HCP Questionnaire: Satisfaction HCP Eligibility Population
Table 3.1	Summary of All Adverse Events by MedDRA SOC and Preferred Term Safety Population

Roche Diabetes Care, Inc

Table No.	Title
Table 3.2.1	Summary of All Adverse Events by Maximum Severity Safety Population
Table 3.2.2	Summary of All Adverse Events by Strongest Causality to Study Device Safety Population
Table 3.2.3	Summary of All Adverse Events Leading to Withdrawal from the Study Safety Population
Table 3.3	Summary of Symptomatic Hypoglycemia, Severe Hypoglycemia and Diabetic Ketoacidosis Safety Population

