7 LISTINGS

Listing No.	Title
Listing 1	Enrollment and Analysis Populations
Listing 2.1	Inclusion Criteria
Listing 2.2	Exclusion Criteria
Listing 3.1	Demographics - Parents/Caregivers
Listing 3.2	Demographics - Child
Listing 3.3	Intervention Group Training
Listing 4	Diabetes Background and History
Listing 5.1	Diabetes Medication
Listing 5.2	Daily Insulin Dose and Boluses
Listing 6	Diabetes Management and Communication
Listing 7	Diabetes Related Absences

Roche Diabetes Care, Inc

Listing No.	Title
Listing 8.1	BG Device Upload Information to eCRF
Listing 8.2	BG Data from Meters/AcuChek-Connect
Listing 8.3	Summary BG Data
Listing 9.1.1	Problem Areas in Diabetes (PAID) - Parents of Youth (YP) - Part 1
Listing 9.1.2	Problem Areas in Diabetes (PAID) - Parents of Youth (YP) - Part 2
Listing 9.2.1	Problem Areas in Diabetes (PAID) - Parents of Teens (TP) - Part 1
Listing 9.2.2	Problem Areas in Diabetes (PAID) - Parents of Teens (TP) - Part 2
Listing 9.3.1	Problem Areas in Diabetes (PAID) - Child (C) - Part 1
Listing 9.3.2	Problem Areas in Diabetes (PAID) - Child (C) - Part 2
Listing 9.4.1	Problem Areas in Diabetes (PAID) - Teens (T) - Part 1
Listing 9.4.2	Problem Areas in Diabetes (PAID) - Teens (T) - Part 2
Listing 10	Blood Glucose Monitoring Communication Survey (BGMC)
Listing 11.1.1	Diabetes Family Conflict Scale - Parent (DFCS-Parent) - Part 1
Listing 11.1.2	Diabetes Family Conflict Scale - Parent (DFCS-Parent)-Part 2
Listing 11.2.1	Diabetes Family Conflict Scale - Youth (DFCS-Youth) - Part 1
Listing 11.2.2	Diabetes Family Conflict Scale - Youth (DFCS-Youth)-Part 2
Listing 12	Follow-up Visits
Listing 13.1	Parent Post-Questionnaire - Usability - Meter
Listing 13.2	Parent Post-Questionnaire - Usability - Phone App
Listing 13.3	Parent Post-Questionnaire - Usability - Web Portal
Listing 13.4	Parent Post-Questionnaire - Satisfaction
Listing 13.5	Parent Post-Questionnaire - Preference
Listing 13.6	Parent Post-Questionnaire - Comments

Roche Diabetes Care, Inc

Listing No.	Title
Listing 14.1	Child & 18 Yr Old Post-Questionnaire - Usability - Meter
Listing 14.2	Child & 18 Yr Old Post-Questionnaire - Usability - Phone App
Listing 14.3	Child & 18 Yr Old Post-Questionnaire - Usability - Web Portal
Listing 14.4	Child & 18 Yr Old Post-Questionnaire - Satisfaction
Listing 14.5	Child & 18 Yr Old Post-Questionnaire - Preference
Listing 14.6	Child & 18 Yr Old Post-Questionnaire - Comments
Listing 15.1	Adverse Events - Symptomatic Hypoglycemia

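### The SAP plans only patient incidence for hypoglycaemia and DKA where the protocol specifies episode numbers, which can blunt or hide a difference in recurrent symptomatic hypoglycaemia

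*SAP*

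**What the plan says.** Protocol 11.6 makes two separate commitments. For adverse events in general: "Summaries of incidence rates (frequencies and percentages) of individual AEs by MedDRA System Organ Class and Preferred Term will be prepared". Then, for symptomatic hypoglycaemia, severe hypoglycaemia and diabetic ketoacidosis (DKA): "Episodes (numbers) of the following AEs will be summarized".

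SAP 5.6 uses patient incidence for adverse events in general and uses it again for the three named events: "A separate analysis of the patient incidence of symptomatic hypoglycemia, severe hypoglycemia (SAE), and diabetic ketoacidosis (SAE) will also be presented". It mentions no number of episodes, event rate or exposure time.

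Three other places bear on the point:

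- SAP Section 6, Table 3.3, is titled "Summary of Symptomatic Hypoglycemia, Severe Hypoglycemia and Diabetic Ketoacidosis Safety Population". The title does not say what is counted, and the note at the end of SAP Section 7 places all output templates in a separate document.
- SAP Section 7, Listing 15.1, is titled "Adverse Events - Symptomatic Hypoglycemia".
- Protocol 9.3.1.1, which covers symptomatic hypoglycaemia, says "the following expected AEs will be considered captured expected AEs and the AE Form in the eCRF needs to be completed".

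**The concern.** The SAP changes the measure without saying so. The protocol treats episode numbers as something additional to incidence. In the SAP the additional analysis is incidence once more, restricted to three events.

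The change matters where an event can happen repeatedly to the same child. Patient incidence asks only whether a child had at least one event in six months. If many children in both arms have at least one, the percentages move together near the top of the scale while the number of episodes may differ widely. Hypoglycaemia stands first among the potential risks in Protocol 8.1, and the app under study offers insulin bolus advice (Protocol 3.1). A reader of the report would therefore want to know how many episodes occurred in each arm as well as how many children were affected.

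**Working it through.** **Wording.** Protocol 9.2.2 and 9.2.3 define hypoglycaemia by the single episode, so the episode numbers in Protocol 11.6 are counts of occurrences. SAP 5.6 counts patients. These are different quantities.

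**Inputs from the documents.** Final visit at 24 weeks (Protocol 7.5): 24 × 7 = 168 days, about 5.5 months. Group size 75 evaluable from 100 enrolled (Protocol 11.1), which allows for 1 − 75/100 = 25% drop-out. The 75 reproduces for the primary endpoint: 2 × (1.960 + 0.842)² / 0.460² = 74.2, rounded up to 75. The plan gives no figure for hypoglycaemia or DKA, so 75 serves below only as an illustrative group size.

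**Assumptions.** The documents give neither an episode rate nor its spread between children. Monthly rates of 0.2 to 2 and dispersion k of 0 or 1 are assumed. Clustering by site is ignored.

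**Incidence when the rate doubles.** With mean count m = rate × 5.5:

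- Poisson (k = 0): incidence = 1 − exp(−m)
- Negative binomial, k = 1: incidence = 1 − 1/(1 + m)

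| Episodes per month | m | Poisson | Negative binomial, k = 1 |
|---|---|---|---|
| 0.2 vs 0.4 | 1.1 vs 2.2 | 66.7% vs 88.9% | 52.4% vs 68.8% |
| 0.5 vs 1 | 2.75 vs 5.5 | 93.6% vs 99.6% | 73.3% vs 84.6% |
| 1 vs 2 | 5.5 vs 11 | 99.6% vs 100.0% | 84.6% vs 91.7% |

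The rate ratio is 2 in every row.

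**What this does to a comparison (75 per arm, two-sided 5%).** Take means of 5 vs 10 episodes and k = 1.

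- Incidence: 5/6 = 83.3% vs 10/11 = 90.9%; power 28%.
- Rate: the variance of the log rate ratio is [(1/5 + 1) + (1/10 + 1)]/75 = 0.0307, so the standard error is 0.175. Then ln 2 / 0.175 = 3.96, and 3.96 − 1.96 = 2.00; power 98%.

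**An example with no distribution.** Suppose 45 of 75 children are affected in each arm, with 2 episodes each in one arm and 6 in the other. Incidence is 45/75 = 60% in both arms; the totals are 45 × 2 = 90 and 45 × 6 = 270.

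**Rare events.** With means of 0.05 vs 0.10 and k = 1, incidence is 0.05/1.05 = 4.8% vs 0.10/1.10 = 9.1%. Power is 18% with either measure.

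**Whether another output fills the gap.** Listing 15.1 is a listing of events and gives no summary by arm. The glycaemic endpoint in SAP 3.5.2.2 is compared between arms and is not a yes/no measure: "Hypoglycemia: Percentage of hypoglycemic measurements defined as the number of hypoglycemic readings in the interval", divided by all checks. It differs from an episode count in four ways:

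- It covers short windows: "values between 30 days prior to or on Visit 3 or Visit 4 will be considered Visit 3 or Visit 4 values".
- It is limited to FAS or ITT families, who need Visit 4 questionnaires, with at least 20 days of baseline readings (SAP 4.1, 4.2, 4.6).
- It mixes symptomatic and asymptomatic lows, whereas Protocol 9.2.2 defines symptomatic episodes by symptoms and makes glucose confirmation optional.
- Its denominator depends on how often the child tests.

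**The case against.** The strongest reply is that little is lost. Table 3.3 has a neutral title and its template may contain episode counts. The percentage of low readings is already compared between arms at 3 and 6 months. Serious events are described as uncommon in Protocol 8.1 and are listed individually. The illustration rests wholly on assumed rates, and a Poisson model without variation between children exaggerates saturation.

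Much of this stands, and it rules out four stronger readings that a reader might infer:

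- *That the report will contain no episode counts.* The template was not available, so only the SAP text can be faulted.
- *That incidence will saturate.* No document gives a frequency. In Protocol 9.3 the label of an expected event is a reporting class, not a rate, and the events described there as common are the non-captured ones, which exclude symptomatic hypoglycaemia. With dispersion 1 the doublings remain visible though smaller. The lowest-rate Poisson case (66.7% vs 88.9%) would itself have about 91% power at 75 per arm, ignoring clustering.
- *That the masking applies equally to all three events.* If severe hypoglycaemia and DKA are rare, the two measures give nearly the same answer.
- *That a rate analysis with a cluster-adjusted interval is owed.* Protocol 11.6 asks only for episode numbers.

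The reply does not remove the mismatch between the two texts. Nor does it supply a summary by arm of symptomatic episodes over the whole follow-up.

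**Conclusion.** The discrepancy is certain for all three events: the protocol specifies episode numbers, and the SAP text specifies patient incidence only, without explanation. The consequence is a possibility, and it concerns mainly symptomatic hypoglycaemia. How far incidence would understate a difference cannot be derived from the documents. Under the assumed rates, a doubling ranges from a clear gap of about 22 percentage points (Poisson, 0.2 vs 0.4 per month) to under half a point (Poisson, 1 vs 2 per month). With dispersion 1 the gap is about 16, 11 and 7 points in the three rows. This is a reporting gap in a safety analysis that is cheap to close; it does not affect the primary endpoint.

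**What to change.** Amend SAP 5.6 and the Table 3.3 template to match Protocol 11.6. For each of the three events and each arm, report:

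- number of episodes
- number and percentage of patients with at least one event (keep this column)
- total person-time, with its start and end stated for both arms
- crude episodes per person-month

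Person-time and the crude rate go a little beyond the protocol's wording. They are worth adding because follow-up will vary: SAP 4.5 admits families after one day in the study, Protocol 6.3 withdraws children who start a pump, CGM or remote sharing, and the plan allows for 25% drop-out. A confidence interval or a comparison of rates between arms is optional; if added, it should allow for repeated events within a child and for randomisation by site.

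The cost is an edit to SAP 5.6 and a few table columns. No new data are needed provided that the adverse event forms record each episode. Protocol 9.3.1.1 implies this but does not state one form per episode, so data management should confirm it.
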